5.2.1. Level of Significance

Statistical tests will be done at a 2-sided significance level of 5%.

Given there is no plan to terminate the study early for favorable efficacy results, no adjustment of the alpha level is considered needed due to the interim analysis.

No multiplicity adjustment will be applied for the secondary endpoints, since this is a non-confirmatory proof-of-concept study.

5.2.2. Pulmonary Function by Spirometry

Pulmonary function will be assessed through spirometry at the study center. All spirometry evaluations should be performed pre-bronchodilator*. Spirometry data taken post-bronchodilator will be excluded from the analysis. Values will be used as provided by the central reading vendor.

* pre-bronchodilator is defined as:

- short-acting more than (>) 6 hours prior to the spirometry assessment
- long-acting bronchodilator at least (\geq) 12 hours prior to the spirometry assessment

Note that a spirometry assessment with no use of bronchodilator is equivalent to a pre-bronchodilator assessment.

The data will be coded as “acceptable”, “borderline acceptable” and “unacceptable”.

“Unacceptable” values will be excluded from analyses. The following quality grades as provided in the database will be used.

Table 3 Spirometry Quality Grades Based on Acceptability and Repeatability criteria

Quality	Criteria
Acceptable	≥ 3 efforts that meet the American Thoracic Society / European Respiratory Society (ATS/ERS) Guidelines (Raghu, Collard, Egan, & al, 2011; Raghu, Remy-Jardin, Myers, Richeldi, & Ryerson, 2018) and the criteria for Acceptability and Repeatability
Borderline acceptable	≥ 2 efforts that meet the ATS/ERS Guidelines and the criteria for Acceptability and Repeatability, or ≥ 3 efforts that meet the ATS/ERS Guidelines and the criteria for Acceptability but not Repeatability
Unacceptable	≤ 1 effort that meets the ATS/ERS Guidelines and the criteria for Acceptability and Repeatability
Acceptability:	

- Time to Peak Expiratory Flow < 250 ms
 - Absence of artifact or cough
 - Exhalation \geq 6 seconds however demonstrated a 1 second plateau
 - Lack of technical problems during effort
- Repeatability:
- Will be based on the computer selected Best effort (highest) compared to next Best effort (second highest) based upon FVC values to be within 150 ml or within 100 ml when FVC \leq 1L

Source: Pulmonary Function Test (PFT) OverRead Guidelines for GLPG1205-CL-220

The following parameters will be presented as part of the spirometry assessment:

- FVC (mL)
- Percent predicted FVC (%)
- FEV₁ (mL)
- Percent predicted FEV₁ (%)
- FEV₁/FVC ratio
- FEF₂₅₋₇₅

Derived values:

- Change from baseline:
Change at time point t = (time point t value) – (baseline value)
- Percent change from baseline:
Percent change at time point t = 100 x (change at time point t) / (baseline value)

For each of the spirometry parameters, descriptive statistics will be provided for the actual values, changes and percent change from baseline per time point and per treatment group. Results will also be graphically displayed by means of subject profile plots, boxplots over time by treatment group for the actual values, and line plots of the mean (+/- SE) over time by treatment group for change from baseline, and percent change from baseline.

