- Safety blood/urine samples for clinical laboratory evaluations and physical examination, vital signs, 12-Lead ECG need to be available at the latest on Day -1
- Repeat spirometry can only proceed if IPF diagnosis per HRCT/LB is confirmed (according to the criteria in [Appendix 1](#))
- For sites that do not have a DLCO machine and need to refer to another site, it is recommended to perform the DLCO only once IPF diagnosis per HRCT/LB is confirmed (according to the criteria in [Appendix 1](#))
- If there is no historical HRCT available, a new HRCT needs to be planned and performed. Only if for logistic reasons it is not possible to perform a new HRCT within the planned screening period and after approval of the medical monitor it is allowed to extend the screening period with maximum 2 weeks

During the baseline visit (Visit 2) the following should be taken into account with respect to the timing of assessments:

- At baseline (Visit 2) all assessments are to be performed prior to dosing
- Spirometry* can be repeated once if confirmation acceptability and repeatability criteria as specified by ATS/ERS/JRS/ALAT are not met. This repeat spirometry must be performed before randomization

– [REDACTED]

- * Spirometry assessments should be performed prebronchodilator. Prebronchodilator spirometry is defined as spirometry testing performed for a subject who has:
- withheld their short-acting β -agonist (e.g. albuterol) or anticholinergic (e.g. ipratropium bromide) for >6 hours prior to the spirometry assessment AND
 - withheld their long-acting bronchodilator (e.g. salmeterol, formoterol) for ≥ 12 hours and other longer-acting agents (e.g. indacaterol, tiotropium) for ≥ 24 hours prior to the spirometry assessment

In case the subject is on bronchodilators, he/she can use the bronchodilator after spirometry assessments

Safety assessments should be repeated at other time points and additional assessments made if clinically indicated.

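### The SAP's pre-bronchodilator filter omits the protocol's 24-hour tier for longer-acting agents, so FVC values that fail the protocol's measurement definition can be kept

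*SAP*

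**What the plan says.** Protocol 6.1 requires spirometry to be prebronchodilator and defines the term by three conditions that must all hold:

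- short-acting β-agonist or "anticholinergic (e.g. ipratropium bromide) for >6 hours prior to the spirometry assessment";
- the subject has "withheld their long-acting bronchodilator (e.g. salmeterol, formoterol") for at least 12 hours;
- "other longer-acting agents (e.g. indacaterol, tiotropium") withheld for at least 24 hours.

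Protocol 6.2 adds a conduct remedy: if a bronchodilator was taken before the test, the visit should be rescheduled within its window.

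SAP 5.2.2 turns the definition into a data filter: "Spirometry data taken post-bronchodilator will be excluded from the analysis". Its definition has only two lines: "short-acting more than (>) 6 hours prior to the spirometry assessment", and "long-acting bronchodilator at least" "12 hours prior to the spirometry assessment". It has no 24-hour line.

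SAP 2.4 says that the SAP is based on protocol version 3.0. Neither the visible part of the SAP version history nor that of SAP 5.5, which lists changes to the planned analyses and is partly redacted, mentions this difference.

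**The concern.** The filter decides which FVC values count. It acts on baseline FVC (SAP 3.3.3, the mean of the pre-dose values), on the observed-case ANCOVA for the primary endpoint (SAP 5.2.2.1), and on the random-slope and repeated-measures sensitivity models (SAP 5.2.2.2). For one named class of agents, the two documents disagree on whether a value obtained 12 to under 24 hours after dosing is valid.

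An affected value at Week 26 and not before, or the reverse, adds a change from baseline that reflects bronchodilator timing and not disease. The two time points are also not treated alike. Baseline averages all pre-dose values, while Week 26 normally uses the single value closest to the target day. An error at Week 26 therefore enters at full weight, and an error in one pre-dose value is diluted.

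The Per-Protocol analysis is not a dependable backstop. It is planned only if at least 10% of subjects are omitted, and it depends on which deviations are classed as major.

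**Working it through.** **1. Classification of a test after a longer-acting agent (indacaterol, tiotropium)**

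| Hours since dose | Protocol 6.1 | SAP 5.2.2 |
|---|---|---|
| under 12 | not prebronchodilator | excluded |
| 12 to under 24 | not prebronchodilator | kept |
| 24 or more | prebronchodilator | kept |

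The documents differ only in the middle row. Reading the SAP's long-acting class as covering both protocol classes does not remove the difference, because it still applies 12 hours where the protocol sets 24.

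**2. The plan's own design figures**

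Inputs from Protocol 7.1: 40 and 20 subjects, 10% dropout (36 and 18 left), SD 200 mL, true differences of 50 and 80 mL in a 50:50 mix.

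- Average effect = 0.5 × 50 + 0.5 × 80 = 65 mL.
- SE = 200 × √(1/36 + 1/18) = 57.7 mL.
- P(observed > 40 mL) = 1 − Φ((40 − 65)/57.7) = 66.8%; the protocol states 67%.
- P(observed > 20 mL) = 1 − Φ((20 − 65)/57.7) = 78.2%; the protocol states 78%.

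Both reproduce. The missing tier changes neither the sample size nor these stated probabilities.

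**3. Illustration of size**

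The documents do not say how many subjects use these agents or how far FVC moves when the washout is short, so the inputs in this step are assumptions. Let d be the difference between arms in the net share of affected Week 26 values, and s the shift per affected value. Then bias in the treatment difference = d × s.

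| d | s | Bias | P(observed > 40 mL), effect masked / inflated |
|---|---|---|---|
| 0 | 50 or 100 mL | 0 | 67% / 67% |
| 5 points | 50 mL | 2.5 mL | 65% / 68% |
| 10 points | 100 mL | 10 mL | 60% / 73% |
| 20 points | 100 mL | 20 mL | 53% / 78% |

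A 10 mL bias is 10/57.7 = 0.17 of the design SE. For a single Week 26 value shifted by 100 mL, the unadjusted arm mean moves by 100/18 = 5.6 mL on placebo or 100/36 = 2.8 mL on GLPG1205. If one of two pre-dose values is shifted by 100 mL, that subject's baseline moves by 50 mL.

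**4. Cost of excluding values**

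The primary analysis is observed-case. If exclusions removed a further 10% of evaluable subjects at Week 26 (assumed), 32.4 and 16.2 would remain, and SE = 200 × √(1/32.4 + 1/16.2) = 60.9 mL, up from 57.7 mL.

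**The case against.** The best defence is that the 24-hour rule still governs conduct. Sites follow Protocol 6.1, and the SAP's schedule of assessments refers to that section for procedures. Protocol 6.2 tells sites to reschedule when a bronchodilator was taken. A discordant value arises only if the subject did not withhold the agent and the visit was not rescheduled. The trial is also randomised and double-blind, and nothing in the documents suggests that such lapses would favour one arm. This stands, and it limits the likely size. It does not remove the point: the SAP filter is there for tests where conduct fails, and for these agents it has a 12-hour gap.

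A reader might infer more than the documents support:

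- **That the gap arises routinely**, because visits are preferably in the morning and an evening dose falls 12 to 24 hours earlier. Nothing in the documents gives evening dosing, the number of users or adherence, and an evening user is told to withhold for 24 hours. If the gap were routine, it would also recur at screening, baseline and Week 26 and largely cancel in the change from baseline.
- **That the SAP defeats an exclusion planned in the protocol.** The protocol contains no such exclusion. It defines how spirometry is done and when to reschedule, and its slope analysis (7.3.4.1) uses all available FVC values. The exclusion is a rule of the SAP, which does not match the protocol's measurement definition.
- **That the protocol labels these values post-bronchodilator.** It defines only prebronchodilator; the values fail that definition.
- **That such values certainly enter the analysis.** They enter only if they occur.

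**Conclusion.** The mismatch is real and undeclared in the visible text. As written, the SAP would keep FVC values obtained 12 to under 24 hours after a longer-acting agent, although they do not meet the protocol's definition of prebronchodilator spirometry. Confidence is high on the wording and low on the consequence.

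The impact is probably small. The 0 to 20 mL range of bias rests wholly on assumed shares and shifts, and any non-zero value needs an imbalance between blinded arms. With balance, the expected bias is about zero and only noise is added. It is still worth correcting, because the rule selects values for the primary endpoint in a trial with about 18 evaluable placebo subjects, and because leaving it open invites a choice after unblinding about which values count. No position is taken here on which interval is pharmacologically right.

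**What to change.** Reconcile SAP 5.2.2 with Protocol 6.1 before unblinding, in one of two ways:

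- let the exclusion filter use the protocol's own three-tier definition, by adding the line for longer-acting agents such as indacaterol and tiotropium; or
- if the two-tier rule is intended, list it in SAP 5.5 as a departure from the protocol and give the reason.

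Aligning the filter costs one line of text and one derivation condition, but two consequences should be accepted openly. A few values may be excluded, and because the primary analysis is observed-case, a subject whose only value in the Week 26 window is excluded drops from that time point. The derivation also needs the agent and the time of its last dose for each spirometry. The protocol provides for recording bronchodilator use (4.3.4.2 and 5.5), but its visible text does not show that this timing is captured, so that should be checked first.

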5.2.2.1. Primary Endpoint: Change from Baseline in FVC over 26 Weeks

The change from baseline in FVC over 26 weeks will be compared between treatment groups by means of an analysis of covariance (ANCOVA) model at each planned time point (as specified in Section 2.5 and 3.3.3) including treatment, sex, and stratum as categorical covariates and age, height, and baseline FVC value as continuous covariates. LS means and 95% CIs will be presented per time point and treatment group as well as the LS mean differences between treatment groups with 95% CI.

Missing data will not be imputed and thus this analysis is conducted on OC only.

Percent predicted FVC will be analyzed using a similar ANCOVA model.

5.2.2.2. Sensitivity Analyses to the Primary Analysis

The following sensitivity analyses are planned to investigate the impact of missing data and protocol violators. If during the blinded review of the data more sensitivity analyses are deemed necessary these will be added to this SAP before unblinding for the final analysis of the CSR.

5.2.2.2.1. Linear Mixed Model

A random coefficient regression model including sex, and stratum as categorical fixed effects and age, and height as continuous fixed effects and a random intercept and slope will be used to analyze the yearly rate of decline in FVC. The treatment effect will be determined by using estimated slopes for each study group on the basis of the time-by-treatment interaction term from the mixed model. The model will be fit using the SAS Proc Mixed procedure, details are in Appendix II. The assumptions of the model will be investigated graphically.

This approach provides another estimate for the primary endpoint. In addition, this model implicitly takes into account missing data under the assumption of missing-at-random (MAR).

5.2.2.2.2. Repeated Measures Analysis

The change from baseline in FVC over 26 weeks will also be compared between treatment groups by means of a mixed effect repeated measures model (MMRM) including sex, stratum and a treatment-by-time point interaction (planned time points as specified in Section 2.5 and 3.3.3) as categorical fixed effects, age, height, and baseline FVC as continuous fixed effects and correlated within-subject residuals. LS means and 95% CIs will be presented per time point and treatment group as well as the LS mean difference with 95% CI. The model will be fit using the SAS Proc Mixed procedure, details are in Appendix II.

This approach provides another estimate for the primary endpoint. In addition, this model implicitly takes into account MAR.

5.2.2.2.3. Per-Protocol Analysis

To investigate the impact of non-compliance and protocol violators a Per-Protocol analysis may also be performed for the primary endpoint using the ANCOVA model described in Section 5.2.2.1. Protocol violations potentially impacting the results will be excluded and identified before database lock and unblinding for the final analysis.

This Per-Protocol analysis is only planned if at least 10% of the subjects are omitted from the Per-Protocol Analysis Set.

This approach provides another estimate than the primary one, namely the estimate in the population of subjects who follow procedures according to protocol.

5.2.2.2.4. Impact COVID-19

To investigate the impact on the primary endpoint of V9 assessments being assigned to the W30 analysis window due to COVID-19, a sensitivity analysis in which these assessments are assigned to the W26 analysis window will be performed for the descriptive statistics, the summary plots over time and the ANCOVA model described in Section 5.2.2.1.

5.2.3. Secondary Endpoints

5.2.3.1. Time to Major Events

A time to (first) event analysis will be conducted for major events, defined as

- Death (all-cause and respiratory-related)
- Hospitalization (all-cause and respiratory-related)

Deaths and hospitalizations will be adjudicated by the CEAC. The analysis will be based on the results from the adjudication, not on the investigator-reported information. Differences will be investigated and listed, if any.

The number and proportion of subjects with an event during the study will be summarized per treatment group. Treatment effect on time to first event will be assessed using the log-rank test. In addition, time to first event will be graphically displayed and tabulated (at each planned time point as described in Section 3.3.3, Week 2, Week 4, etc, and last available time point) per treatment group using Kaplan-Meier estimates.

In addition, for all-cause hospitalization and all-cause mortality a frequency table will be provided for the event classification categories as determined by the CEAC. These categories are described in the CEAC charter.

Censoring

Time-to-event endpoints are defined from the date of first dose of study medication.

If the subject did not have an event, the time to event will be censored at the last contact date, as defined in Section 3.4.1.3.

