4.4. MEASURES TO MINIMIZE BIAS

4.4.1. Randomization

At screening, subjects will be assigned a subject identification number using a centralized electronic system (interactive web response system [IWRS]). When subjects are confirmed to be eligible for the clinical study, the subject will be randomized in a 2:1 ratio to GLPG1205 or placebo. Allocation of each subject to a given treatment will be done via IWRS and will be stratified for background standard of care (subjects receiving nintedanib, pirfenidone, or neither nintedanib nor pirfenidone).

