7.3.4.2. Secondary Efficacy Endpoints Analyses

The % predicted FVC change from baseline will be analyzed using a similar model as the one described for the primary analysis.

The proportions of subjects who have an absolute decline of 10 percentage points or more in % predicted FVC or who die will be analyzed using logistic regression.

Treatment effect on time to death (all cause and respiratory-related) / hospitalization (all cause and respiratory-related), whichever occurs first, will be assessed using the log-rank test. Kaplan-Meier estimates will be derived for probability of death (all cause and respiratory-related) / hospitalization (all cause and respiratory-related) (whichever occurs first) over time and displayed graphically.

SGRQ total score and domains will be analyzed using descriptive statistics of actual values and changes from baseline at all time points. The proportion of SGRQ responders (defined as absolute change from baseline at all time points, in SGRQ total score \leq -4 points) will also be tabulated.

SGRQ responders and proportion of subjects with hospitalization will be described and tested for treatment differences using a Fisher's exact test.

More detail will be provided in the SAP.

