3.4.4. Stratification Factors

The analyses will be stratified by the type of IPF SOC medication taken at randomization: nintedanib or pirfenidone or neither. In all analyses, except if indicated otherwise, the stratum will be the SOC at randomization and will not change if the subject switches SOC during the study.

The 3 strata could differ in their safety profile, in addition, they might have different effects on the biomarker results (depending on the biomarker) and efficacy results. Therefore, for all analyses, 3 strata will be used (nintedanib, pirfenidone, neither), unless indicated otherwise.

The stratum reported in the case report form (CRF) will be used in the analyses. Any discrepancies in stratification reported in the interactive web response system (IWRS) versus CRF will be listed.

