The proportion of SGRQ responders at Week 26 (defined as absolute change from baseline in SGRQ total score ≤ -4 %, at least once) will also be tabulated per treatment group. Treatment effect on SGRQ responders will be assessed using the Fisher's exact test.

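### SGRQ responders are tested without the SOC strata that SAP 3.4.4 makes the default, and the log-rank section leaves its stratification open: a low-cost improvement for two secondary endpoints

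*SAP*

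**What the plan says.** Protocol 4.4.1: "the subject will be randomized in a 2:1 ratio to GLPG1205 or placebo", with allocation stratified by background SOC in three groups (nintedanib, pirfenidone, neither).

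SAP 3.4.4 sets the general rule: "The analyses will be stratified by the type of IPF SOC medication taken at randomization: nintedanib or pirfenidone or neither". It adds: "for all analyses, 3 strata will be used (nintedanib, pirfenidone, neither), unless indicated otherwise".

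The two secondary tests at issue read as follows.

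- **SGRQ responders**, SAP 5.2.3.3: "Treatment effect on SGRQ responders will be assessed using the Fisher's exact test". Protocol 7.3.4.2 also specifies this: "SGRQ responders and proportion of subjects with hospitalization will be described and tested for treatment differences using a Fisher's exact test".
- **Death or hospitalisation**, SAP 5.2.3.1: "Treatment effect on time to first event will be assessed using the log-rank test". Protocol 7.3.4.2 also names the log-rank test. Neither document calls it stratified or unstratified.

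The SAP's model-based efficacy sections do name the stratum: the FVC ANCOVA (5.2.2.1), the random-slope and repeated-measures models (5.2.2.2.1 and 5.2.2.2.2), the 6MWT ANCOVA (5.2.3.2) and the SGRQ score ANCOVA (5.2.3.3).

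**The concern.** When allocation is balanced within strata and the strata are prognostic, a pooled test still counts the between-stratum spread as noise, although the design has removed it from the treatment comparison. The test then becomes conservative and loses power. Stratifying recovers that power by using groups the trial has already formed.

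There is also a question of reproducibility. Because the models name the stratum and the log-rank section does not, one programmer could run it pooled, while another applying 3.4.4 would stratify. The p-value for the death or hospitalisation endpoint could then depend on a choice made at programming.

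**Working it through.** **The plan's own figure.** The documents give no event rate, responder rate or power for these two tests. The only design figure is for FVC in protocol 7.1. With 40 and 20 subjects less 10% dropout (36 and 18), SE = 200 × √(1/36 + 1/18) = 57.74 mL. The average effect under a 50:50 mix is (50 + 80)/2 = 65 mL. P(observed > 40) = 1 − Φ((40 − 65)/57.74) = 66.7%, and P(observed > 20) = 1 − Φ((20 − 65)/57.74) = 78.2%. These match the stated 67% and 78%, but they say nothing about the tests discussed here.

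**Responder test.** Taken from the documents: 60 subjects, 40:20, three strata, two-sided 5%. Assumed: strata of 30/15/15 (the 50:50 aim in protocol 7.1, with the drug half split equally), 2:1 within each; placebo responder rates as in the table, stratum of 30 first; a common odds ratio (OR). For example, a 25% placebo rate has odds 1/3, so OR 3 gives odds 1, or 50%.

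- Fisher: hypergeometric distribution of GLPG1205 responders in the pooled 40 versus 20 table. The p-value sums all outcomes no more probable than the one observed.
- Exact stratified: same rule, but conditioning on the responder total in each stratum, so the null distribution is the convolution of three hypergeometrics.

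8,000 simulated trials per cell, both tests on the same data (Fisher → exact stratified):

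| Placebo rates | Size | Power, OR 3 | Power, OR 5 |
|---|---|---|---|
| 25/25/25% | 3.9% → 3.9% | 39.0% → 40.2% (+1.2) | 73.8% → 75.0% (+1.2) |
| 20/30/30% | 3.3% → 3.5% | 38.1% → 40.0% (+1.9) | 72.3% → 74.2% (+1.9) |
| 15/35/35% | 3.1% → 3.5% | 33.7% → 37.7% (+4.0) | 66.8% → 72.6% (+5.8) |
| 10/40/50% | 2.0% → 3.1% | 23.6% → 32.6% (+9.0) | 52.2% → 65.2% (+13.0) |

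At OR 4 the gain is about 1 to 3 points in the first two rows, 5 to 6 in the third and 12 to 13 in the last. With about 20 per stratum, the gains over OR 3 to 5 are 0.3 to 1.4, 1.8 to 2.6, 5.4 to 5.8 and 10.7 to 11.8. A stratum of exactly 20 cannot be split 2:1, and results then also depend on which stratum carries the odd subject, so I put more weight on the 30/15/15 layout.

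**Log-rank.** Z² = (Σ(O − E))²/ΣV, with E and V taken from pooled risk sets (plain) or within strata and then summed (stratified); reject above 3.84. Assumed: 30 weeks, 10% random early censoring, placebo 30-week risk of 15% or 30% in a stratum with hazard multiplier 1, and both stratum layouts. 6,000 trials per cell; ranges run over the four combinations of risk and layout:

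| Hazard range across strata | Size, plain | Size, stratified | Power gain in points, HR 0.5 | Power gain in points, HR 0.3 |
|---|---|---|---|---|
| none | 4.5–5.0% | 4.3–5.0% | −0.3 to +0.4 | −0.3 to +0.4 |
| 2-fold | 4.0–4.8% | 4.2–5.3% | +0.4 to +0.9 | +0.3 to +0.7 |
| 4-fold | 3.6–4.2% | 4.4–5.4% | +1.1 to +2.1 | +0.8 to +2.3 |
| 10-fold | 2.8–4.0% | 4.6–5.9% | +1.8 to +4.9 | +2.4 to +6.3 |

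The Monte Carlo standard error is about 0.3 points for size and at most about 0.65 for power.

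**Absolute power.** By Schoenfeld's formula with 2:1 allocation, power = Φ(√(d × 2/9) × |ln HR| − 1.96). With d = 12 assumed events, √(12 × 2/9) = 1.633. HR 0.5 gives Φ(1.132 − 1.96) = 20%, and HR 0.3 gives Φ(1.966 − 1.96) = 50%. Power is limited with either version.

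**The case against.** **The log-rank may already be stratified.** Section 3.4.4 covers all analyses unless indicated otherwise, and 5.2.3.1 indicates nothing otherwise. This stands. A reader might infer from the bare wording that the SAP specifies a plain log-rank and contradicts itself. The documents do not support that: the defect is an ambiguity, created by contrast with the sections that name the stratum.

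**Fisher's test is the protocol's choice.** The SAP follows protocol 7.3.4.2, and naming a specific test could itself count as indicating otherwise. That is a fair reading, but the SAP does not say the exception is deliberate.

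**The loss is conditional.** A reader might infer that these tests are conservative and lose power simply because strata are ignored. The documents do not establish this. SAP 3.4.4 says only that strata might differ in efficacy results. The protocol introduction reports a possible mortality benefit for pirfenidone and a trend for nintedanib, without rates for this population.

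**Fisher is conservative anyway.** Across the two layouts its size is 3.1 to 3.9% with no stratum effect at all, because the test is discrete. The exact stratified test stays at 2.8 to 3.9%. Only the further fall to 2.0 to 2.1% at 10/40/50% can be put down to ignored strata.

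**Small strata might make stratifying costly.** The simulations do not bear this out: with no stratum effect, the log-rank changes by no more than simulation noise and the responder test loses nothing.

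**The endpoints are exploratory.** SAP 5.2.1 calls the study non-confirmatory, and protocol 7.1 reports no formal sample size calculation. This stands and keeps the severity low.

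**Conclusion.** The point holds as a low-severity improvement. Fisher's exact test does not fit the general rule in SAP 3.4.4, and 5.2.3.1 does not settle whether that rule applies to the log-rank.

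For responders, an exact stratified test did at least as well in every scenario run. At OR 4 it gains about 1 to 3 points with no or mild stratum differences and about 5 to 13 with strong ones, with size below 5%. For the log-rank, the gain is about 0 to 2 points up to a 4-fold hazard range. At 10-fold it is larger, but part of it reflects the stratified test's size, which reached 5.9% in one setting. All rates, stratum effects and treatment effects behind these figures are assumptions.

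Nothing here threatens validity, since a conservative test does not inflate false positives.

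**What to change.** 1. **SAP 5.2.3.3:** test SGRQ responders with an exact stratified (Mantel-Haenszel) test by 3-level SOC at randomisation. Keep Fisher's exact test as supportive, which preserves the protocol's analysis, and record the change in SAP 5.5.
2. **SAP 5.2.3.1:** state that the log-rank is stratified by the same factor per 3.4.4, with the unstratified test as supportive.
3. Write out the three levels in both places, because the models in SAP Appendix II code SOC in two. Take the stratum from the CRF, as 3.4.4 already specifies.

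The cost is a line of text and a strata option for each test, settled before unblinding. No new data are needed. A stratum with no events, or with no responders, simply contributes nothing.
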